5.5.7 Concomitant treatment

The investigator should instruct the patient to notify the study site about any new medications he/she takes after the patient was enrolled into the study. All medications, procedures and significant non-drug therapies (including physical therapy, dietary modification, protein supplements and blood transfusions) administered after the patient was enrolled into the study must be recorded on the Concomitant medications eCRF or Surgical and Medical procedures eCRF.

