9.1.2 Concomitant medications

The number and percentage of patients using prior or concomitant medications will be summarized by Anatomical Therapeutic Classification (ATC) codes and treatment group, and grouped by anatomical main group (the 1st level of the ATC codes).

Prior medications are defined as drugs taken and stopped prior to first dose of investigational treatment. Any medication given at least once between the day of first dose of investigational treatment and the date of the last study visit will be a concomitant medication, including those which were started pre-baseline and continued into the treatment period. Prior or concomitant medication will be identified based on recorded or imputed start and end dates of medication taking. If it cannot be established that the use of a prior medication has ended prior to the first dose of investigational treatment due to a missing end date, then it will be considered concomitant.

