- Treatment-emergent: AEs will be deemed treatment-emergent if the date of onset or worsening of the AE is on or after the start of the first infusion of study drug (Day 1) until the last infusion of study drug (expected per protocol at Week 20) + 56 days.
- Concomitant definition: Concomitant medications defined as any medication which started or stopped on or after the start of the first infusion of study drug (Day 1) up to the last infusion of study drug (expected per protocol at Week 20) + 56 days or is ongoing.

In addition, analysis and presentation of patients' data beyond Week 24 (end of defined treatment epoch) will be handled as follows:

- Study drug administration data (Actual exposure to study drug [days] and exposure to study drug [days], cut-off): For pre-amendment 2 patients potentially treated for more than 24 weeks (more than 6 infusions), study drug administration data after Week 20 will be recorded in the Dose administration record – infusion electronic case report form (eCRF). For both pre- and post-amendment 2 patients, exposure to study drug will therefore be summarized by actual exposure days based on overall treatment duration, regardless of the defined 24-week treatment epoch (i.e. disregarding the cut-off at 6 months [24 weeks] treatment) and days exposed within the defined 24-week treatment epoch:
 - Actual exposure: ([Actual last infusion date + 56 days] – First infusion date) + 1 day.
 - Exposure, cut-off: ([Last infusion date, within the 24-week defined treatment epoch + 56 days] – First infusion date) + 1 day.
- DXA assessment data recorded after Week 24, for example at Week 36, Week 48 or Week 52, in the Body composition –DXA eCRF will be listed in by-patient data listings only. Subsequently, if treated for more than 6 months, the defined treatment epoch will comprise the first 24 weeks of treatment only as described above. The change in DXA assessments will be analyzed based on the first 24 weeks of treatment only as applied for all patients in the study, whether they were randomized pre- or post-amendment 2.

The same conventions and definitions will be applied whether the patient completes treatment or prematurely discontinues treatment or study. Similarly, regardless if the analysis is performed at the time of the primary or final update analysis.

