2.9.2 Concomitant and post-treatment medications

The number (n) and percentage (%) of patients taking concomitant or post-treatment medications will be summarized by Anatomical Therapeutic Chemical (ATC) classification and PT, by treatment group and across all four treatment groups combined for patients assigned to the SAF analysis set, overall only. Medications will be presented alphabetically by anatomical main group (the 1st level of the ATC code). Within each ATC Level 1, the PTs will be sorted by descending frequency of the total number of patients with at least one medication in each PT. In the event of PTs with equal total frequencies, the relevant PTs will be sorted alphabetically. The number (n) and percentage (%) of patients having at least one concomitant or post-treatment medication in each ATC Level 1 and PT will be presented. Hence if a patient reported more than one concomitant or post-treatment medication with the same PT, the concomitant or post-treatment medication will be counted only once. Similarly, if a patient reported more than one concomitant or post-treatment medication within the same primary ATC Level 1, the patient will be counted only once. The overall number (n) and

percentage (%) of patients receiving at least one medication and receiving at least one medication in each level of summarization will be presented relative to the total number of patients in the SAF analysis set and relative to the medication category (concomitant/post-treatment) (see [Section 2.4](#) [Formal planned analyses]).

Medications will be categorized as follows:

- Concomitant medications: Defined as any medication which started or stopped on or after the start of the first infusion of study drug up to the last infusion of study drug (expected per protocol at Week 20) + 56 days or is ongoing (see [Section 2.3](#) [Treatment pooling and handling of pre-amendment 2 patients]).
- Post-treatment medications: Defined as any medication which started or stopped after the last infusion of study drug (expected per protocol at Week 20) + 56 days or is ongoing (a medication can therefore be flagged as both concomitant and post-treatment) (see [Section 2.3](#) [Treatment pooling and handling of pre-amendment 2 patients]).

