Concomitant and post-treatment medications will be identified based on recorded or imputed start and end dates of medication taken. If it cannot be established that the use of a prior medication has ended prior to the start of the first infusion of study drug due to a missing end date, then it will be considered concomitant. Algorithms for date imputations will be provided in RAP Module 8 (Programming Specifications).

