2.9.3 Prior, concomitant and post-treatment surgical or medical procedures

The number (n) and percentage (%) of patients with prior, concomitant or post-treatment surgical and medical procedures will be summarized in separate tables, as relevant according to MedDRA SOC and PT, regardless of whether the status is reported as ongoing or not. Surgical and medical procedures will be presented by treatment group and across all four treatment groups combined for patients assigned to the SAF analysis set, overall only. Primary SOCs will be sorted alphabetically and within each primary SOC, the PTs will be sorted by descending order of total frequency. In the event of PTs with equal total frequencies, the relevant PTs will be sorted alphabetically. The number (n) and percentage (%) of patients having at least one surgical or medical procedure, and having at least one surgical or medical procedure in each primary SOC and PT will be presented. Hence if a patient reported more than one surgical or medical procedure with the same PT, the surgical or medical procedure will be counted only once. Similarly, if a patient reported more than one surgical or medical procedure within the same primary SOC, the patient will be counted only once at the SOC level. The overall number (n) and percentage (%) of patients having at least one surgical or medical procedure and at least one surgical or medical procedure in each level of summarization will be presented for patients in the SAF analysis set entering treatment (+ 56-days) or post-treatment follow-up, as relevant (see [Section 2.4](#) [Formal planned analyses]).

Surgical and medical procedures will be categorized as follows:

- Prior surgical and medical procedure: Defined as a surgical or medical procedure started and stopped prior to the start of the first infusion of study drug.
- Concomitant surgical and medical procedure: Defined as any surgical or medical procedure which started or stopped on or after the start of the first infusion of study drug up to the last infusion of study drug (expected per protocol at Week 20) + 56 days or is ongoing (see [Section 2.3](#) [Treatment pooling and handling of pre-amendment 2 patients]).

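### Read literally, the SAP's concomitant rule leaves out treatments begun before first infusion, used throughout dosing and stopped after last infusion + 56 days, and adds treatments begun after that point that are still ongoing

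*SAP*

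**What the plan says.** SAP 2.9.2 gives the concomitant medication rule: "Defined as any medication which started or stopped on or after the start of the first infusion of study drug up to the last infusion", with the window closing at last infusion + 56 days. SAP 2.3 states the same rule and ends it "expected per protocol at Week 20) + 56 days or is ongoing". SAP 2.9.3 carries the form over to procedures: "Defined as any surgical or medical procedure which started or stopped on or after the start of the first infusion". There are thus three routes to the flag: a start inside the window, a stop inside the window, or ongoing status. The ongoing route carries no condition on the start date.

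The post-treatment rule in SAP 2.9.2 covers a start or stop after last infusion + 56 days, "or is ongoing (a medication can therefore be flagged as both concomitant and post-treatment". A separate sentence handles uncertain cases: "If it cannot be established that the use of a prior medication has ended prior to the start of the first infusion" because the end date is missing, the drug is treated as concomitant.

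Protocol 9.1.2 tests for use instead: "Any medication given at least once between the day of first dose of investigational treatment and the date of the last study visit" is concomitant, and drugs begun before baseline and carried into treatment are expressly included. Protocol 5.5.7 requires "significant non-drug therapies (including physical therapy, dietary modification, protein supplements and blood transfusions" to be recorded on the medication or procedure forms, so physiotherapy falls under one of the two SAP rules.

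**The concern.** A concomitant table should show what patients were receiving while on study drug. The SAP rule asks instead whether a record began or ended in the window. A treatment that spans the whole window does neither. Unless it is still ongoing, it drops out of the table, although it was in use on every treatment day.

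Background care here is local (protocol 5.1.2.1) and includes pain treatment and osteoporosis prevention. Physiotherapy and nutritional supplements are also recorded. First dose is timed close to the start of physical therapy (protocol 3.3), and SAP 2.8.2.3.1 collects physiotherapy given before first infusion, so treatments that begin before Day 1 are expected. The tables in SAP 2.9.2 and 2.9.3 help a reader judge whether the arms received similar background treatment during dosing. Omitting spanning treatments and adding late starters blurs that comparison.

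**Working it through.** **Inputs.** First infusion F = Day 1. The last infusion is at Week 20, target Day 140, and End of Study is at target Day 336 (SAP Table 3.1). The window end is W = 140 + 56 = Day 196 for a completer. The follow-up epoch starts after Week 24 (Day 168), so its first 196 − 168 = 28 days lie inside the window.

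**Rules**, for a record with start s and end e:

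- SAP concomitant: F ≤ s ≤ W, or F ≤ e ≤ W, or ongoing.
- SAP post-treatment: s > W, or e > W, or ongoing.
- Overlap with the SAP window: s ≤ W and (e ≥ F or ongoing).
- Protocol 9.1.2: any use from F to the last study visit.

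A start can fall before, in or after the window. An end can fall in the same three places or be ongoing. Since the end cannot precede the start, nine patterns are possible.

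| Start | End | Example (days) | SAP concomitant | SAP post-treatment | Overlap | Protocol 9.1.2 |
|---|---|---|---|---|---|---|
| before | before | −20 to −5 | no | no | no | no |
| before | in | −20 to 100 | yes | no | yes | yes |
| **before** | **after** | **−20 to 250** | **no** | **yes** | **yes** | **yes** |
| before | ongoing | −20, ongoing | yes | yes | yes | yes |
| in | in | 180 to 190 | yes | no | yes | yes |
| in | after | 50 to 250 | yes | yes | yes | yes |
| in | ongoing | 50, ongoing | yes | yes | yes | yes |
| after | after | 250 to 260 | no | yes | no | yes |
| **after** | **ongoing** | **250, ongoing** | **yes** | **yes** | **no** | **yes** |

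The SAP rule and the overlap rule differ in exactly two patterns. Running both rules over start and stop days from Day −40 to Day 336, in two-day steps, found the same two and no others.

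- *Before to after.* The SAP misses it, while overlap and the protocol both count it. The missing-end-date sentence does not help, because the end date is known. Under SAP 2.9.3 such a procedure is not prior either, because prior requires it to have stopped before first infusion.
- *After, ongoing.* The SAP counts it although it was never in use inside the SAP's window. The protocol also counts it, because its window runs to the last study visit.

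SAP 2.14 has a general entry on epoch presentation, but nothing on the start-or-stop wording or on the end of the concomitant window.

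**The case against.** **Intended meaning.** If ongoing means in use at the end of the window, both anomalies disappear. The missing-end-date sentence and the definition of prior procedures suggest that the authors had use in mind. But the SAP does not define the term that way, and in SAP 2.9.3 it treats ongoing as a reported record status. A programmer following the text would produce the table above.

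**Limited consequence.** The flag feeds descriptive safety-set tables only. The efficacy models do not use it, and per-protocol exclusions come from the protocol deviation data (SAP 3.10). Missed records still appear by arm as post-treatment and in listings. Counting is by patient within term or class, so another qualifying record of the same term keeps the patient in the count. Patients who discontinue treatment early have their End of Study visit about 28 + 28 = 56 days after last infusion (protocol 5.5.9), so the window covers nearly all of their stay. All of this stands, and it makes the point small.

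**Stronger readings that the documents do not support.**

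- A reader might infer that anything first started in follow-up is flagged concomitant. Only treatments that start after about Day 196 and are still ongoing are added against the SAP's window. A start between Day 169 and Day 196 is inside it, and one that starts and stops after it is not flagged.
- A reader might infer that adding late starters breaches the protocol. Protocol 9.1.2 would count them too.
- A record that is ongoing at the primary analysis can lose its concomitant flag at the final update, once a stop date is entered. A reader might see a breach of the SAP 2.3 statement that the same conventions hold at both. The convention is the same and the data have been updated. SAP 2.4.1 says that analyses of concomitant medication are not final at the primary analysis.
- Days 197 to 336 are 140 of 336 study days, or 42%. A reader might take that as the share of records or patients affected. It is a share of calendar time only.
- A reader might assume that physiotherapy courses from before Day 1 to beyond Day 196 are typical, or that these tables are the only evidence on background care. No document says how long courses last, and pre-dose physiotherapy has its own summary.

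**Conclusion.** The rule is wrong as written, in a limited way. Read literally, it leaves out of the concomitant tables any treatment that begins before first infusion and has a known stop after last infusion + 56 days. For medications this contradicts protocol 9.1.2, and SAP 2.14 does not declare it. The protocol section speaks of medications only, so for procedures the fault is that the rule misses treatment in use throughout the SAP's own window. The rule also adds treatments that begin after the window and are still ongoing, which is an inconsistency within the SAP.

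The harm is wrong entries in descriptive tables, mainly for completers. The number of affected records cannot be derived. The conclusion assumes that ongoing is a record status and that the last infusion falls near Day 140. For other patients the same logic holds with their own last infusion date.

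**What to change.** In SAP 2.3, 2.9.2 and 2.9.3, define concomitant by overlap:

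- start date ≤ last infusion + 56 days, AND
- end date ≥ first infusion date, or end date missing, or ongoing.

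Keep the post-treatment definition, so that a treatment can still carry both flags. Add an entry to SAP 2.14 saying that the concomitant window ends at last infusion + 56 days, whereas protocol 9.1.2 runs to the last study visit. The entry is needed because the overlap rule still departs from the protocol for treatments first started after the window, and for late starters that are ongoing it moves further from the protocol than the present wording does.

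The cost is a line of text in each of three sections, one entry in 2.14, and a small change to the derivation code. No new data are needed, and the other seven patterns keep their present classification.

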2.9.3 Prior, concomitant and post-treatment surgical or medical procedures

The number (n) and percentage (%) of patients with prior, concomitant or post-treatment surgical and medical procedures will be summarized in separate tables, as relevant according to MedDRA SOC and PT, regardless of whether the status is reported as ongoing or not. Surgical and medical procedures will be presented by treatment group and across all four treatment groups combined for patients assigned to the SAF analysis set, overall only. Primary SOCs will be sorted alphabetically and within each primary SOC, the PTs will be sorted by descending order of total frequency. In the event of PTs with equal total frequencies, the relevant PTs will be sorted alphabetically. The number (n) and percentage (%) of patients having at least one surgical or medical procedure, and having at least one surgical or medical procedure in each primary SOC and PT will be presented. Hence if a patient reported more than one surgical or medical procedure with the same PT, the surgical or medical procedure will be counted only once. Similarly, if a patient reported more than one surgical or medical procedure within the same primary SOC, the patient will be counted only once at the SOC level. The overall number (n) and percentage (%) of patients having at least one surgical or medical procedure and at least one surgical or medical procedure in each level of summarization will be presented for patients in the SAF analysis set entering treatment (+ 56-days) or post-treatment follow-up, as relevant (see [Section 2.4](#) [Formal planned analyses]).

Surgical and medical procedures will be categorized as follows:

- Prior surgical and medical procedure: Defined as a surgical or medical procedure started and stopped prior to the start of the first infusion of study drug.
- Concomitant surgical and medical procedure: Defined as any surgical or medical procedure which started or stopped on or after the start of the first infusion of study drug up to the last infusion of study drug (expected per protocol at Week 20) + 56 days or is ongoing (see [Section 2.3](#) [Treatment pooling and handling of pre-amendment 2 patients]).

- Post-treatment surgical and medical procedure: Defined as any surgical or medical procedure which started or stopped after the last infusion of study drug (expected per protocol at Week 20) + 56 days or is ongoing (see [Section 2.3](#) [Treatment pooling and handling of pre-amendment 2 patients]).

Prior, concomitant or post-treatment surgical and medical procedures will be identified based on recorded or imputed start and end dates of the surgical and medical procedure. If it cannot be established that the surgical and medical procedure has ended prior to the start of the first infusion of study drug due to a missing end date, then it will be considered concomitant. Algorithms for date imputations will be provided in RAP Module 8 (Programming Specifications).

2.10 Efficacy evaluation

See [Appendix 1](#) (Efficacy assessments: Performance and assessment details) for details of the relevant efficacy assessments.

The primary analysis set for all proposed efficacy analyses is the FAS. The primary analysis will be repeated for the PP analysis set as confirmation of the primary analysis results.

The bimagrumab 700 mg, bimagrumab 210 mg and placebo treatment groups will be used for formal hypothesis testing. The bimagrumab 70 mg treatment group will only be used for the purpose of conducting formal dose-response modeling as described in [Section 2.10.1.6](#) (Supportive analysis), even though the lower dose will be included in all descriptive summaries of primary, secondary and other secondary [REDACTED] efficacy variables.

2.10.1 Analysis of the primary efficacy variable

2.10.1.1 Variable

The primary efficacy variable is the change from Baseline in the total LBM (kg), (whole body) (referred to as total LBM) at Week 24. Total LBM (kg) will be recorded at Day 1 (+ 2-day window), Week 12 and Week 24 (EOT).

2.10.1.2 Descriptive presentations

Descriptive statistics (see [Section 3.2](#) [Precision and summary statistics]) for total LBM (kg) will be presented on the original scale for all patients assigned to FAS, at each windowed visit and change from Baseline at each windowed post-baseline visit and End of Treatment (derived) as relevant. All summaries will be presented for each treatment group and across active bimagrumab treatment groups combined (“Active Total: Efficacy” – Includes bimagrumab 700 mg and bimagrumab 210 mg treatment groups only), overall and by the following [REDACTED] subgroups as detailed in [Section 2.6](#) (Subgroups):

- Region (Japan/Non-Japan).
- [REDACTED]
- Fracture fixation type (internal [screws only, intramedullary {nails} and extramedullary fixation {plate, combinations}]/arthroplasty [hemiarthroplasty or total hip arthroplasty]).
- History of falls (yes/no [none]).
- Use of mobility aids prior to hip fracture (yes/no [none]).

- 25OH Vitamin D at Screening (< 30 nmol/L [<12 ng/mL] / \geq 30 nmol/L [<12 ng/mL]).
- Amendment (pre-amendment 2/post-amendment 2).

For patients enrolled post-amendment 2 a subgroup presentation by Region (Japan/non-Japan) will also be displayed.

Similarly, the mean change in total LBM (kg) from Baseline at each windowed post-baseline visit including End of Treatment (derived) and the associated 95% confidence interval of the mean change in total LBM (kg) will be presented graphically, on the original scale, by treatment group and “Active Total: Efficacy”, overall and by the [REDACTED] subgroups specified above (see [Section 2.6](#) [Subgroups]), repeating also by Region only for patients enrolled post-amendment 2.

2.10.1.3 Statistical model, hypothesis, and method of covariate analysis

The primary efficacy objective of the study is to show that at least one bimagrumab treatment group (bimagrumab 700 mg and/or bimagrumab 210 mg) will increase total LBM (kg) (change from Baseline) compared to placebo at Week 24 by rejecting the null hypothesis described below at significance level $\alpha=0.05$ level (two-sided):

$$H_0: \mu_T = \mu_P \text{ versus } H_1: \mu_T \neq \mu_P$$

where μ_T and μ_P are the mean change from Baseline in total LBM (kg) at Week 24 for bimagrumab treatment groups (bimagrumab 700 mg, bimagrumab 210 mg) and placebo treatment group respectively.

A mixed model repeated measures (MMRM) will be used to test the hypothesis with change from Baseline at all windowed post-baseline visits (Week 12 and Week 24) as response variable, and treatment group, visit, region (Japan/Non-Japan), treatment date (early/late) and Baseline total LBM (kg) as covariates (see “Covariates” column of Table 2.2 [[Section 2.6](#) {Subgroups}]).

In addition, the following four interaction terms will be fitted:

Treatment group*visit.

Region*visit.

Treatment date*visit.

Baseline total LBM*visit.

An unstructured within patient correlation structure will be used for the covariance matrix. The Kenward-Roger approximation will be used to estimate denominator degrees of freedom. Residual/restricted maximum likelihood (REML) method will be used to estimate parameters. The total LBM (kg) will be transformed by using natural logarithm prior to calculating the change from Baseline and performing any analysis. The covariate, Baseline total LBM (kg) will also be log transformed. The antilog of the point estimate and associated 95% confidence interval of the treatment difference will be computed prior to presentation. The two-sided p-value for the exponential (exp) least squares mean, $\exp(\text{LSM})$, ratio (%) between each of the two bimagrumab treatment groups and placebo at Week 24 and at Week 12 will be reported. The Holm-Bonferroni method will be used to adjust the Type I error for the two comparisons

(bimagrumab 700 mg versus placebo and bimagrumab 210 mg versus placebo) treatment group at Week 24. No control for multiplicity will be made at Week 12. Although not part of the formal hypothesis testing, the two-sided p-value for the LSM difference between “Active Total: Efficacy” and placebo at Week 24 and at Week 12 will also be reported.

